#### 6.2 Preparation/Handling/Storage/Accountability

#### 6.2.1 Dose Preparation

There are no specific calculations or evaluations required to be performed in order to administer the proper dose to each participant. The rationale for selection of doses to be used in this study is provided in Section 4.3.

#### 6.2.2 Handling, Storage, and Accountability

The investigator or designee must confirm appropriate temperature conditions have been maintained during transit for all study intervention received, and any discrepancies are reported and resolved before use of the study intervention.

Only participants enrolled in the study may receive study intervention, and only authorized site staff may supply or administer study intervention. All study interventions must be stored in a secure, environmentally controlled, and monitored (manual or automated) area in accordance with the labeled storage conditions with access limited to the investigator and authorized site staff.

The investigator, institution, or the head of the medical institution (where applicable) is responsible for study intervention accountability, reconciliation, and record maintenance (ie, receipt, reconciliation, and final disposition records).

For all study sites, the local country Sponsor personnel or designee will provide appropriate documentation that must be completed for drug accountability and return, or local discard and destruction if appropriate. Where local discard and destruction is appropriate, the investigator is responsible for ensuring that a local discard/destruction procedure is documented.

The study site is responsible for recording the lot number, manufacturer, and expiry date for any locally purchased product (if applicable) as per local guidelines unless otherwise instructed by the Sponsor.

The investigator shall take responsibility for and shall take all steps to maintain appropriate records and ensure appropriate supply, storage, handling, distribution, and usage of study interventions in accordance with the protocol and any applicable laws and regulations.

## 6.3 Measures to Minimize Bias: Randomization and Blinding

#### 6.3.1 Intervention Assignment

Intervention randomization will occur centrally using an IRT system. There are 2 study intervention arms. Participants will be assigned randomly in a 1:1 ratio to suvorexant and placebo, respectively.

#### 6.3.2 Stratification

Intervention randomization will be stratified according to the following factors:

1. Hospitalization reason (acute disease, elective surgery)

If either the proportion of participants hospitalized due to acute disease or those hospitalized due to elective surgery exceeds approximately 60% of the total targeted sample size, the remaining participants will only be enrolled into the other stratum within this stratification factor.

2. Age category (<75 years,  $\geq 75$  years)

#### 6.3.3 Blinding

A double-blinding technique with in-house blinding will be used. MK-4305 and placebo will be packaged identically so that blind is maintained. The participant, the investigator, and Sponsor personnel or delegate(s) who are involved in the study intervention administration or clinical evaluation of the participants are unaware of the intervention assignments.

See Section 8.1.14 for a description of the method of unblinding a participant during the study should such action be warranted.

#### 6.4 Study Intervention Compliance

Interruptions from the protocol-specified intervention plan for  $\geq 2$  days in total require consultation between the investigator and the Sponsor and written documentation of the collaborative decision on participant management.

#### 6.5 Concomitant Therapy

Medications specifically prohibited in the exclusion criteria are not allowed during time periods specified by this protocol for that medication. If there is a clinical indication for any medication specifically prohibited, discontinuation from study intervention may be required. The investigator should discuss any questions regarding this with the Sponsor Clinical Director. The final decision on any supportive therapy rests with the investigator and/or the participant's primary physician. However, the decision to continue the participant on study intervention requires the mutual agreement of the investigator, the Sponsor, and the participant.

The use of concomitant medications and medications that may cause delirium should be limited to a bare minimum to minimize the impact on efficacy and safety assessment.

# 6.5.1 **Prohibited Therapy**

From 2 weeks before Randomization to the end of the assessment period

- Hypnotics (including prescription Chinese herbs, and other than study medications)
- Antipsychotics
- Mood stabilizers
- Antidepressants
- Anxiolytics
- Psychostimulants
- Anticonvulsants
- Tiapride

#### From the day of Randomization to the end of the assessment period

• Strong CYP3A inhibitors

Examples: Itraconazole, clarithromycin, ritonavir, nelfinavir, voriconazole, and posaconazole.

#### From 30 days before Screening to the end of the study

• Other investigational medications

The use of these prohibited medications including antipsychotics for treatment of delirium is allowed in the opinion of the investigator after completion or following a decision of discontinuation of study medications administration.

## 6.5.2 Rescue Medications and Supportive Care

No rescue or supportive medications are specified for use in this study.

#### 6.6 **Dose Modification**

No dose modifications are permitted in this study.

## 6.7 Intervention After the End of the Study

There is no study-specified intervention following the end of the study.

#### 6.8 Clinical Supplies Disclosure

The emergency unblinding call center will use the intervention randomization schedule for the study to unblind participants and to unmask study intervention identity. The emergency unblinding call center should only be used in cases of emergency (see Section 8.1.14). The Sponsor will not provide random code/disclosure envelopes or lists with the clinical supplies.

See Section 8.1.14 for a description of the method of unblinding a participant during the study should such action be warranted.

## 7 DISCONTINUATION OF STUDY INTERVENTION AND PARTICIPANT WITHDRAWAL

#### 7.1 Discontinuation of Study Intervention

Discontinuation of study intervention does not represent withdrawal from the study.

As certain data on clinical events beyond study intervention discontinuation may be important to the study, they must be collected through the participant's last scheduled followup, even if the participant has discontinued study intervention. Therefore, all participants who discontinue study intervention prior to completion of the protocol-specified intervention period will still continue to participate in the study as specified in Section 1.3 and Section 8.9.3.

Participants may discontinue study intervention at any time for any reason or be discontinued from the study intervention at the discretion of the investigator should any untoward effect occur. In addition, a participant may be discontinued from study intervention by the investigator or the Sponsor if study intervention is inappropriate, the study plan is violated, or for administrative and/or other safety reasons. Specific details regarding procedures to be performed at study intervention discontinuation are provided in Section 8.1.13 and Section 8.9.3.

A participant must be discontinued from study intervention but continue to be monitored in the study for any of the following reasons:

- The participant or participant's legally acceptable representative requests to discontinue study intervention.
- Developing delirium as assessed by DSM-5

After randomization, when the qualified rater judges that a participant developed delirium as assessed by DSM-5.

• Adverse events

In the case that the investigator assesses that administration of the study medication should be discontinued due to the occurrence of adverse experiences.

#### PRODUCT: MK-4305 PROTOCOL/AMENDMENT NO.: 085-03

Protocol Violation

It becomes inappropriate to continue study intervention as a result of a significant protocol deviation.

• Non-Compliance with Study Drug

When a participant has not agreed with or followed the instructions related to the study medication, or a study intervention is not initiated on the day of Randomization.

• In addition, the investigator and/or the Sponsor judges that participant should discontinue the study medications for any other reason.

Example: When a participant has either transferred to another hospital after the initiation of study medication and is no longer able to participate in the study.

The study procedures of assessment period after discontinuation from study intervention are not performed, since the objectives of this study is to investigate the efficacy of suvorexant on reduction in incidence of developing delirium.

Discontinuation from study intervention is "permanent." Once a participant is discontinued from study intervention, they shall not be allowed to restart study intervention.

#### 7.2 Participant Withdrawal From the Study

A participant must be withdrawn from the study if the participant or participant's legally acceptable representative withdraws consent from the study.

If a participant withdraws from the study, they will no longer receive study intervention or be followed at scheduled protocol visits.

Specific details regarding procedures to be performed at the time of withdrawal from the study, are outlined in Section 8.1.13. The procedures to be performed should a participant repeatedly fail to return for scheduled visits and/or if the study site is unable to contact the participant are outlined in Section 7.3.

#### 7.3 Lost to Follow-up

If a participant fails to return to the clinic for a required study visit and/or if the site is unable to contact the participant, the following procedures are to be performed:

- The site must attempt to contact the participant and reschedule the missed visit. If the participant is contacted, the participant should be counseled on the importance of maintaining the protocol-specified visit schedule.
- The investigator or designee must make every effort to regain contact with the participant at each missed visit (eg, telephone calls and/or a certified letter to the participant's last

known mailing address or locally equivalent methods). These contact attempts should be documented in the participant's medical record.

• Note: A participant is not considered lost to follow-up until the last scheduled visit for the individual participant. The missing data for the participant will be managed via the prespecified statistical data handling and analysis guidelines.

## 8 STUDY ASSESSMENTS AND PROCEDURES

- Study procedures and their timing are summarized in the SoA.
- Adherence to the study design requirements, including those specified in the SoA, is essential and required for study conduct.
- The investigator is responsible for ensuring that procedures are conducted by appropriately qualified (by education, training, and experience) staff. Delegation of study site personnel responsibilities will be documented in the Investigator Trial File Binder (or equivalent).
- All study-related medical decisions must be made by an investigator who is a qualified physician.
- All screening evaluations must be completed and reviewed to confirm that potential participants meet all eligibility criteria. The investigator will maintain a screening log to record details of all participants screened and to confirm eligibility or record reasons for screening failure, as applicable.
- Procedures conducted as part of the participant's routine clinical management (eg, blood count) and obtained before signing of ICF may be utilized for screening or baseline purposes provided the procedure met the protocol-specified criteria and were performed within the time frame defined in the SoA.
- Additional evaluations/testing may be deemed necessary by the investigator and or the Sponsor for reasons related to participant safety. In some cases, such evaluation/testing may be potentially sensitive in nature (eg, HIV, Hepatitis C), and thus local regulations may require that additional informed consent be obtained from the participant. In these cases, such evaluations/testing will be performed in accordance with those regulations.

Repeat or unscheduled samples may be taken for safety reasons or for technical issues with the samples.

## 8.1 Administrative and General Procedures

## 8.1.1 Informed Consent

The investigator or medically qualified designee (consistent with local requirements) must obtain documented informed consent from each potential participant (and their legally acceptable representative as needed) prior to participating in this clinical study. If there are

changes to the participant's status during the study (eg, health or age of majority requirements), the investigator or medically qualified designee must ensure the appropriate documented informed consent is in place.

# 8.1.1.1 General Informed Consent

Informed consent given by the participant (and their legally acceptable representative as needed) must be documented on a consent form. The form must include the study protocol number, study protocol title, dated signature, and agreement of the participant (and his/her legally acceptable representative as needed) and of the person conducting the consent discussion.

A copy of the signed and dated informed consent form should be given to the participant before participation in the study.

The initial ICF, any subsequent revised ICF, and any written information provided to the participant must receive the IRB/IEC's approval/favorable opinion in advance of use. The participant, and his/her legally acceptable representative as needed, should be informed in a timely manner if new information becomes available that may be relevant to the participant's willingness to continue participation in the study. The communication of this information will be provided and documented via a revised consent form or addendum to the original consent form that captures the participant's dated signature, and by the participant's legally acceptable representative's dated signature as needed.

Specifics about the study and the study population are to be included in the study informed consent form.

Informed consent will adhere to IRB/IEC requirements, applicable laws and regulations, and Sponsor requirements.

## 8.1.2 Inclusion/Exclusion Criteria

All inclusion and exclusion criteria will be reviewed by the investigator to ensure that the participant qualifies for the study.

# 8.1.3 Participant Identification Card

All participants will be given a participant identification card identifying them as participants in a research study. The card will contain study site contact information (including direct telephone numbers) to be used in the event of an emergency. The investigator or qualified designee will provide the participant with a participant identification card immediately after the participant provides documented informed consent. At the time of intervention randomization, site personnel will add the treatment/randomization number to the participant identification card.

The participant identification card also contains contact information for the emergency unblinding call center so that a healthcare provider can obtain information about study intervention in emergency situations where the investigator is not available.

# 8.1.4 Medical History

The investigator will review a medical history including a history of delirium in any prior hospitalization.

# 8.1.5 Prior and Concomitant Medications Review

# 8.1.5.1 **Prior Medications**

The investigator will review prior medication use, and record prior medication taken by the participant within 30 days before Screening.

# 8.1.5.2 Concomitant Medications

The investigator will record medication, if any, taken by the participant during the study.

# 8.1.6 APACHE II

The investigator will assess APACHE II [Knaus WA, et al. 1985] for participants hospitalized due to acute disease and confirm the eligibility of the enrollment.

Procedures conducted after the admission as part of the participant's routine clinical management (e.g., the measurement of vital signs and laboratory tests) and obtained before signing of ICF may be utilized for the assessment of APACHE II.

# 8.1.7 ECOG PS

The investigator will assess ECOG PS [Oken MM, et al. 1982] for participants hospitalized due to acute disease and confirm the eligibility of the enrollment.

## 8.1.8 NM Scale

The investigator will assess the cognitive function using NM scale [Otsuka T, et al. 1991] for all participants and refer to the assessment at the enrollment (mild cognitive impairment or severity of dementia).

# 8.1.9 Non-pharmaceutical Therapy

According to Section 5.3.1, the non-pharmaceutical therapy to be performed (See Table 2) will be confirmed and it will be mentioned in the medical record. From the day of Randomization to the end of the assessment period, the investigator and/or the site staff will conduct the non-pharmaceutical therapy per the nursing plan.

The investigator will confirm whether non-pharmaceutical therapy had been conducted per the nursing plan and record it.

## 8.1.10 Assignment of Screening Number

All consented participants will be given a unique screening number that will be used to identify the participant for all procedures that occur prior to randomization. Each participant will be assigned only 1 screening number. Screening numbers must not be re-used for different participants.

## 8.1.11 Assignment of Treatment/Randomization Number

All eligible participants will be randomly allocated and will receive a treatment/randomization number. The treatment/randomization number identifies the participant for all procedures occurring after treatment randomization. Once a treatment/randomization number is assigned to a participant, it can never be re-assigned to another participant.

A single participant cannot be assigned more than 1 treatment/randomization number.

# 8.1.12 Study Intervention Administration

Each participant will take the first dose before bedtime on the day of randomization.

If the rater judges a participant develop delirium after randomization and before the first dose, the participant must discontinue the study without taking study medication.

## 8.1.12.1 Timing of Dose Administration

From the day of randomization, each participant will take one tablet of study medication once daily orally before bedtime for 5-7 days in double-blind manner according to the individuals' hospitalization duration. On the day of the last assessment visit, the study medication should not be administered.

If the participant missed a dose of study medication, the missed dose of last night should not be administered and one tablet of study medication should be administered before the next bedtime. The study medication must not be taken upon awakening in the middle of the night, even if the participant failed to take study medication at bedtime that previous night. Two or more tablets of the study medication must not be taken a night.

If the participant is not able to take study medication due to his/her condition, the investigator should inform the Sponsor promptly and discuss the continuation of study medications administration of this participant with the Sponsor.

#### 8.1.13 Discontinuation and Withdrawal

Participants who discontinue study intervention prior to completion of the assessment period should be encouraged to complete the follow-up visit as outlined in the SoA and Section 8.9.3.

Participants who withdraw from the study should be encouraged to complete all applicable activities scheduled for the last assessment visit at the time of withdrawal. Any AEs that are present at the time of withdrawal should be followed in accordance with the safety requirements outlined in Section 8.4.

## 8.1.14 Participant Blinding/Unblinding

STUDY INTERVENTION IDENTIFICATION INFORMATION IS TO BE UNMASKED ONLY IF NECESSARY FOR THE WELFARE OF THE PARTICIPANT. EVERY EFFORT SHOULD BE MADE NOT TO UNBLIND.

For emergency situations where the investigator or medically qualified designee (consistent with local requirements) needs to identify the intervention used by a participant and/or the dosage administered, he/she will contact the emergency unblinding call center by telephone and make a request for emergency unblinding. As requested by the investigator or medically qualified designee, the emergency unblinding call center will provide the information to him/her promptly and report unblinding to the Sponsor. Prior to contacting the emergency unblinding call center to request unblinding of a participant's intervention assignment, the investigator who is a qualified physician should make reasonable attempts to enter the intensity of the AEs observed, the relation to study intervention, the reason thereof, etc., in the medical chart. If it is not possible to record this assessment in the chart prior to the unblinding, the unblinding should not be delayed.

In the event that unblinding has occurred, the circumstances around the unblinding (eg, date, reason, and person performing the unblinding) must be documented promptly, and the Sponsor Clinical Director notified as soon as possible.

Participants whose treatment assignment has been unblinded by the investigator or medically qualified designee and/or nonstudy treating physician must be discontinued from study intervention, but should complete the follow-up visit.

#### 8.1.15 Hospitalization

The participants hospitalized due to acute disease will be randomized within 24 hours after admission to the clinical site.

The participants hospitalized due to elective surgery will be admitted to the clinical site on the day or 2 days before the surgery AND before randomization on the day of the first dose of study medication. If the scheduled date of the surgery is changed by any reasons after randomization, the investigator should contact the Sponsor promptly to discuss whether the participant should continue the study or not.

PRODUCT: MK-4305 PROTOCOL/AMENDMENT NO.: 085-03

The participant will be hospitalized for 6 days and 5 nights from the day of the first dose of study medication or longer in cases of acute disease OR elective surgery scheduled on the next day after admission/Day 1, OR, for 7 days and 6 nights in cases of elective surgery scheduled 2 days after admission/Day 1. In the case that the hospitalization duration from the day of the first dose of the study medication is for over 7 days, the intervention duration will be for 7 days.

# 8.1.16 Calibration of Equipment

The investigator or qualified designee has the responsibility to ensure that any device or instrument used for a clinical evaluation/test during a clinical study that provides information about inclusion/exclusion criteria and/or safety or efficacy parameters shall be suitably calibrated and/or maintained to ensure that the data obtained are reliable and/or reproducible. Documentation of equipment calibration must be retained as source documentation at the study site.

## 8.2 Efficacy Assessments

The raters of DSM-5 and DRS-R-98 must receive the training provided by the Sponsor and meet the qualification before rating of this study. The rater qualifications, training and applicable certification process are established in a separate document. The rater should assess according to the manuals as a separate document. To minimize variability, it is preferred that the same rater(s) perform the same evaluation(s) for each participant during the study.

## 8.2.1 DSM-5

During the assessment period, the qualified rater will review the medical record including the nursing record and question from the participant. The necessary information for the assessment will be collected from the family of the participant and/or the site staff as well, as needed. Based on this information, the rater will assess whether the participant had developed delirium or not as measured by DSM-5 since the last assessment once daily in morning at least, and will record it. DSM-5 assessment should be performed anytime if the rater finds symptoms of suspected delirium in the participant. Assessing DSM-5, the information for assessment of DRS-R-98 should be referred, in principle. If assessing that the participant develops delirium during the assessment period, the subtype and causes of delirium (using the etiology checklist [Trzepacz PT, et al. 2009]) will be assessed, they will be recorded.

If the rater assess that the participant developed delirium as measured by DSM-5, that should be entered in AE eCRF as well.

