# 8.4.6 Disease-related Events and/or Disease-related Outcomes Not Qualifying as AEs or SAEs

There are no disease-related events and/or disease-related outcomes not qualifying as AEs or SAEs in this study. Note that delirium as measured by DSM-5 should be reported as an AE eCRF as well, if the investigator assesses that the participant developed delirium as measured by DSM-5.

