#### 9.5 Analysis Populations

#### 9.5.1 Efficacy Analysis population

The FAS population will serve as the primary population for the analysis of efficacy data in this study. The FAS population consists of all randomized participants who have at least one assessment of delirium by DSM-5 following administration of at least one dose of study medication. Occurrences of delirium after randomization but prior to the first dose of study medication will thus be excluded from the analysis.

A supportive analysis using the Per-Protocol (PP) population may be performed for the primary efficacy endpoint if there is a substantial number of protocol violators (>10% of FAS) that will be excluded from the PP population. The PP population excludes participants due to major deviations from the protocol that may substantially affect the results of the primary efficacy endpoint. Potential deviations that may result in the exclusion of a participant from the PP population include:

- Significant violation to the inclusion/exclusion criteria that may affect the results of the primary efficacy endpoint
- Missing assessment of delirium by DSM-5 at any time during the assessment period
- Treatment duration of less than 5 days, with the exception of discontinuation due to delirium as assessed by DSM-5
- Missed dose(s) of study treatment at any time during the trial
- Use of prohibited concomitant medications

The final determination on major protocol deviations, and thereby the composition of the PP population, will be made prior to the unblinding of the database and will be documented in a separate memo.

Participants will be included in the treatment group to which they are randomized for the analysis of efficacy data.

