# 9.6.2 Statistical Methods for Safety Analyses

The analysis of safety results will follow a tiered approach (Table 6). The tiers differ with respect to the analyses that will be performed. AEs (specific terms as well as system organ class terms) and events that meet predefined limits of change (PDLCs) in laboratory and vital sign parameters are either pre-specified as "Tier 1" endpoints, or will be classified as belonging to "Tier 2" or "Tier 3" based on the number of participants with events.

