#### Tier 2 events

Tier 2 parameters will be assessed via point estimates with 95% CIs provided for differences in the proportion of participants with events (also via the unstratified Miettinen and Nurminen method).

Membership in Tier 2 requires that at least 4 participants in any treatment group exhibit the event. The threshold of at least 4 events was chosen because the 95% CI for the between-group difference in percent incidence will always include zero when treatment groups of equal size each have less than 4 events and thus would add little to the interpretation of potentially meaningful differences. Because many 95% confidence intervals for Tier 2 events may be provided without adjustment for multiplicity, the CIs should be regarded as a helpful descriptive measure to be used in review, not a formal method for assessing the statistical significance of the between-group differences in adverse events and safety parameters that meet predefined limits of change.

In addition to individual events that occur in 4 or more participants in any treatment group, the broad AE categories consisting of the proportion of participants with any AE, a drug related AE, a serious AE, an AE which is both drug-related and serious, and discontinuation of study medication due to an AE will be considered Tier 2 endpoints.

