#### Continuous safety measures

For continuous measures such as changes from baseline in laboratory and vital sign parameters, summary statistics for baseline, on-treatment, and change from baseline values will be provided by treatment group in table format.

Safety Tier	Safety Endpoint	p-Value	95% CI for Treatment Difference	Descriptive Statistics
Tier 1	Complex sleep-related behaviors			
	Sleep paralysis (including sleep onset paralysis [adjudicated])			
	Hypnagogic or hypnopompic hallucinations			
	Somnolence resulting in discontinued intervention	Х	Х	Х
	Falls (adjudicated to rule out cataplexy)			
	Suicidal ideation and/or behaviors			
	Selected events associated with potential for abuse			
	Cataplexy (adjudicated)			
Tier 2	Any AE †			
	Any drug-related AE			
	Any serious AE			
	Any drug-related serious AE		Х	Х
	Discontinuation of study medication due to AE			
	Specific AEs, SOCs, or PDLCs (incidence $\geq 4$			
	participants in at least one of the treatment groups)			
Tier 3	Specific AEs, SOCs or PDLCs ‡ (incidence <4			
	participants in all of the treatment groups)			Х
	Change from Baseline Results (Labs, Vital Signs)			
	tes broad AE category of the number of participants re			
‡ Includ	es only those endpoints not pre-specified as Tier 1 or :	not already p	pre-specified as Tier 2	endpoints

Table 6Analysis Strategy for Safety Parameters

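### The Tier 2 any-AE row and the SOC row holding delirium include the primary efficacy event, and this protocol and SAP specify no companion row without it

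*Combined protocol and SAP*

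**What the plan says.** Section 9.4.1 makes the proportion with DSM-5 delirium during the assessment period the primary efficacy endpoint. Section 8.2.1 sends the same event to the safety database: "If the rater assess that the participant developed delirium as measured by DSM-5, that should be entered in AE eCRF as well". Section 8.4.6 repeats the instruction and closes off any exemption: "There are no disease-related events and/or disease-related outcomes not qualifying as AEs or SAEs in this study". Section 8.4.1 collects all AEs from randomization to 14 days after dosing stops, which covers the whole assessment period.

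Section 9.6.2 applies its tiers to individual AE terms and to SOC terms. Tier 2 gives a difference and an unstratified Miettinen-Nurminen 95% CI for any term or SOC reaching 4 participants in a group. It also gives these for "the broad AE categories consisting of the proportion of participants with any AE" and four further broad categories: drug-related, serious, drug-related serious, and stopping study medication because of an AE. On the status of the intervals it says "the CIs should be regarded as a helpful descriptive measure to be used in review". Neither the text nor the legible part of Table 6 removes delirium from a row or plans a second version without it. The supplemental SAP is mentioned for supportive and exploratory efficacy methods, extra subgroups and later non-confirmatory changes. No sentence assigns it a delirium-free AE row.

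**The concern.** Safety and tolerability is a primary objective in Section 3, with adverse events as an endpoint. The any-AE row is usually the first one read for that objective. Here it mixes two questions: whether the drug prevents delirium, and whether participants otherwise tolerate it. If suvorexant works as planned, the row favours it even when every other AE is equally common in both arms. A diffuse excess of other AEs could likewise be offset in the aggregate. The SOC row has the same feature, with probably fewer other events to dilute it.

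**Working it through.** **1. The plan's own figure.** Section 9.9.1 gives 90% power at 11.6% vs 30% with 100 per arm, two-sided 0.05. The mean rate is 0.208, so z = [0.184 × √100 − 1.96 × √(2 × 0.208 × 0.792)] / √(0.116 × 0.884 + 0.30 × 0.70) = (1.840 − 1.125) / 0.559 = 1.279, and power is 89.95%. The figure reproduces. These are the delirium rates used below. Both the delirium term (about 12 and 30 per 100) and its SOC pass the Tier 2 threshold of 4.

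**2. Any AE with no difference in other AEs.** Let d be the delirium rate and o the rate of other AEs. The documents give no o for this trial, so it is an assumption shown over a range. With o equal in both arms and independent of delirium, P(any AE) = d + (1 − d) × o, and the gap is (0.30 − 0.116) × (1 − o).

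| o | Suvorexant | Placebo | Gap in favour of suvorexant (points) |
|---|---|---|---|
| 20% | 29.3% | 44.0% | 14.7 |
| 50% | 55.8% | 65.0% | 9.2 |
| 70% | 73.5% | 79.0% | 5.5 |
| 80% | 82.3% | 86.0% | 3.7 |
| 90% | 91.2% | 93.0% | 1.8 |

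**3. What the planned interval would show.** Unstratified Miettinen-Nurminen 95% CI, 100 per arm, counts rounded from the model:
- o = 20%: 29 vs 44, −15.0 (−27.9 to −1.6)
- o = 25%: 34 vs 48, −14.0 (−27.2 to −0.3)
- o = 30%: 38 vs 51, −13.0 (−26.3 to 0.8)
- o = 50%: 56 vs 65, −9.0 (−22.3 to 4.6)
- o = 80%: 82 vs 86, −4.0 (−14.4 to 6.3)

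The interval excludes zero up to a background of about 25% and not at 30%.

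**4. Dependence.** Suppose other AEs are 1.5 times as likely in participants with delirium, with the same overall rate m in both arms. The rate without delirium is m / (1 + 0.5d), and P(any AE) = d + (1 − d) × m / (1 + 0.5d). Results are 28.3 vs 42.2% (gap 13.9) at m = 20%, 53.4 vs 60.4% (7.1) at 50%, and 70.1 vs 72.6% (2.5) at 70%. The rate with delirium cannot exceed 100%, so m ≤ (1 + 0.5d) / 1.5. That is 70.5% on suvorexant and 76.7% on placebo. The scenario therefore fails above about 70.5% and says nothing about 80 to 90%.

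**5. SOC row.** The documents give no background for this SOC. If 10% have another event in it, the row reads 20.4 vs 37.0%. For 20 vs 37 of 100 the difference is −17.0 (−29.1 to −4.5).

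**6. Can the missing row be rebuilt?** Take the 50% case: any AE 56 vs 65, delirium 12 vs 30. The number with some other AE lies between 56 − 12 = 44 and 56 on suvorexant, and between 65 − 30 = 35 and 65 on placebo. Those two rows alone allow a difference anywhere from 44 − 65 = −21 to 56 − 35 = +21. Other term rows can narrow this range but do not give the proportion, because one participant can appear in several.

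**The case against.** The strongest reply is that nothing here is an error. Delirium is a harm, Section 8.4.6 counts it as an AE by deliberate choice, and fewer AEs because of less delirium is a true result for any AE. That stands, and so does the point about consequence. Tier 2 intervals are descriptive and carry no p-value or decision. The eight Tier 1 events are tested one by one. Delirium has its own term row, and an any-drug-related-AE row is planned. That last row separates tolerability only partly, since an investigator may judge a delirium case drug-related. A high background is also plausible in acutely ill or surgical participants followed to 14 days after dosing; at 70 to 90% the gap is 5.5 to 1.8 points. What remains is step 6: the planned rows do not yield the proportion with any AE other than delirium.

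Three stronger readings are tempting and not supported:
- A reader might infer that the any-AE row will look significantly favourable whatever the tolerability. That needs a background of about 25% or less, which the documents neither give nor imply.
- A reader might infer that a harm is being hidden. Nothing shows one. Section 4.3.1 reports comparable AE incidence in elderly insomnia patients, although that is a different population.
- A reader might extend the point to the Table 6 row "Discontinuation of study medication due to AE". Section 7.1 lists "Developing delirium as assessed by DSM-5" and adverse events as separate reasons for stopping. Section 9.5.1 sets a treatment-duration criterion "with the exception of discontinuation due to delirium as assessed by DSM-5", and Section 9.6.3 displays the reasons for discontinuation. Delirium stops are thus already a separate, displayed reason, and a further row of them would nearly repeat the primary endpoint.

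**Conclusion.** The point holds as a cheap improvement of low severity. That the two rows contain the primary efficacy event follows from the text and needs no assumption. The size does: it rests on the planned 11.6% vs 30%, an assumed background of other AEs, and independence or the one dependence case shown. Under independence it runs from 14.7 points at a 20% background to 1.8 at 90%. The SOC figure rests on an assumed 10% background. The absence of a companion row is established only for this protocol and SAP, since the supplemental SAP could not be checked. No efficacy conclusion is affected, and neither the AE recording nor the planned rows are wrong.

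**What to change.** In Section 9.6.2 and Table 6, keep all planned rows and leave AE recording as it is. Before unblinding, add two supplementary Tier 2 rows by the same method: any AE excluding DSM-5 delirium, and the affected SOC excluding DSM-5 delirium. Each should be read beside its all-AE row, with neither taken as the sole basis for a conclusion.

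State the downside with them. Delirium ends dosing under Section 7.1, so at the planned rates about 30% of placebo and 11.6% of suvorexant participants stop for it. The new rows therefore compare arms with unequal exposure, and they include AEs arising after delirium.

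The cost is two summary rows from data already collected, with no change to conduct or to the primary analysis.
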